6 HAZARDS/DISCOMFORTS/RISKS

6.1 DRUGS

6.1.1 Sofosbuvir

SOF is an FDA-approved medication for the treatment of HCV. As per the package insert, common side-effects of SOF therapy include, but are not limited to fatigue, headache, dizziness, and nausea. There may be additional side effects of SOF that are not yet known. SOF has been administered to over 10,000 subjects in combination with a DAA, Peg-IFN, and/or RBV in Gilead's clinical development programs as of July 2015. No clinical safety issues related to SOF have been identified to date.

6.1.2 Velpatasvir

In early studies done on those with HCV using VEL, participants experienced mild to moderate headache (20%), frequent daytime urination (20%), and upper respiratory infection. Other side effects seen less frequently were drowsiness, nausea and dizziness, which were seen in the same frequency as the group taking a placebo. In healthy volunteers, the following mild side effects were seen in more than two participants: headache, chest pain, feeling hot, constipation, rash with itching, and upper respiratory infection. One participant had more serious abdominal pain, but also had a history of abdominal pain prior to the study. No significant laboratory changes occurred in either group requiring any type of intervention. There may be additional side effects of VEL that are not yet known.

The safety profile of the regimen of SOF 400 mg and VEL 100 mg administered for 12 weeks has been established in approximately 230 subjects enrolled in Phase 2 studies. No clinical safety issues specifically related to VEL or SOF+VEL have been identified to date.

6.1.3 Voxilaprevir

To date, over 2600 subjects have received SOF/VEL+VOX in the Phase 1, 2, and 3 studies and there have been no clinical safety issues identified. There is no expectation of significant overlapping or new, unexpected toxicities upon coformulation of SOF/VEL with VOX as an FDC; data from study GS-US-367-1176 comparing SOF/VEL+VOX with SOF/VEL/VOX were consistent with this. However, a potential risk of the study includes the identification of previously undetected adverse effects.

6.1.4 Resistance

There is a potential risk for subjects to develop multiclass resistance if treatment in this study is unsuccessful. However, VOX has the highest reported barrier to resistance among NS3/4A PIs and so the anticipated clinical risk of developing drug-resistant mutants with VOX is anticipated to be lower than that associated with first and second generation NS3/4A PIs Accordingly, there was a lack of any viral breakthrough during therapy with VOX in the 3-day monotherapy study. Mutants generated in vitro to be resistant to VOX remain sensitive to SOF and GS-5816, supporting the clinical use of VOX in combination with other classes of HCV inhibitors. Lastly, this risk is balanced by the high efficacy shown in evaluations of SOF/VEL/VOX in Phase 2 studies and a very low rate of emergent resistance among subjects who relapsed.

Development of such resistance could affect future therapeutic options. However all efforts will be made to manage the development of class specific mutations that could lead to cross resistance to other NS5B, NS5A, and NS3 inhibitors.

6.2 **PROCEDURES**

6.2.1 Phlebotomy

The primary risks of phlebotomy include occasional bleeding or bruising of the skin at the site of needle puncture, and the sensation of transient lightheadedness or rarely, fainting and infection. The amount of blood drawn will be within the limits allowed for adult subjects (450 ml over 6 weeks).

6.2.2 Electrocardiogram

This will be performed at screening for all participants and if medically indicated while on study. Subjects may experience itching, redness or irritation at the site of the electrodes.

6.2.3 Liver Biopsy

Liver biopsies performed within 36 months prior to Day 0, either the University of Maryland or outside institutions, will be acceptable as inclusion criteria based upon the written pathology report.

If a liver biopsy is required for inclusion, it can be performed as part of the screening process. A separate procedure consent will be obtained prior to each liver biopsy. An ultrasound of the liver or other imaging will only be performed if medically indicated prior to biopsies. Subjects will be admitted and released after the procedure according to the site policies for subjects receiving conscious sedation. The adverse effects of liver biopsy include both early and late manifestations. All side effects will be recorded and classified as minor and major complications. The minor complications include pain and vasovagal reaction. The major complications include clinically significant hemorrhage, bowel perforation, infection, pneumothorax, and rarely death. All subjects will be followed as outpatients after discharge from the site so as to detect any major late manifestations of complications associated with liver biopsy.

7 BENEFITS/COMPENSATION/ALTERNATIVES

7.1 **BENEFITS**

Subjects may have the benefit of suppression and in some cases eradication of hepatitis C virus. Study drugs and study-related routine clinical monitoring tests will be provided free of charge to all subjects. The results of any specialized tests performed as part of the study will be made available to interested study subjects and their physicians.

In the event of injury occurring as a result of participation in this research study, subjects will be advised to seek immediate necessary medical care from their home physician and to contact the PI. Short-term medical care will be provided, as needed, for such injury. There is no provision for long-term free medical care or for monetary compensation from any injury from the physicians conducting this study, from the Institute of Human Virology, University of Maryland or Gilead Sciences

7.2 ALTERNATIVES

Subjects can receive hepatitis C treatment through their private physician or decide not to be treated at this time.

7.3 COMPENSATION

Subjects will receive remuneration for the immediate costs associated with their study-related expenses like travel expenses, lodging, etc. Subjects will also receive financial compensation for the additional time associated with study related procedures such as research blood draws for the PK/VK sub study and liver biopsy. Subjects will be financially compensated for the inconvenience of the procedures necessary to obtain the samples. The compensation will be as follows:

- Liver Biopsy with research specimens: \$250 cash per biopsy (maximum of 2)
- VK sub study: \$200 cash after completion of all time points.
- Scheduled Study Visits: \$25 cash or grocery gift card for lab visits and \$50 cash or grocery gift card for study visits.

8 ADVERSE EVENTS AND TOXICITY MANAGEMENT

8.1 **DEFINITIONS**

Adverse Event (AE): An adverse event is any untoward or unfavorable medical occurrence in a human subject, including any abnormal sign (e.g. abnormal physical exam or laboratory finding), symptom, or disease, temporally associated with the subject's participation in the research, whether or not considered related to the research.

Serious Adverse Event (SAE):

A Serious Adverse Event is an AE that results in one or more of the following outcomes:

- death
- a life-threatening (i.e., an immediate threat to life) event
- an inpatient hospitalization or prolongation of an existing hospitalization;
- a persistent or significant incapacity or substantial disruption of the ability to conduct normal life functions
- a congenital anomaly/birth defect
- a medically important event*

* Medical and scientific judgment should be exercised in deciding whether expedited reporting is appropriate in other situations, such as important medical events that may not be immediately life threatening or result in death or hospitalization but they may jeopardize the subject or may require intervention to prevent one of the other outcomes listed above.

Unexpected Adverse Event: An AE is unexpected if it is not listed in the Investigator's Brochure or Package Insert (for marketed products) or is not listed at the specificity or severity that has been observed. It is the responsibility of the IND Sponsor to make this determination.

Serious and Unexpected Suspected Adverse Reaction (SUSAR): A SUSAR is a Suspected Adverse Reaction that is both Serious and Unexpected.

Unanticipated Problem That Is Not An Adverse Event (UPnonAE): An unanticipated problem that does not fit the definition of an adverse event, but which may, in the opinion of the investigator, involve risk to the subject, affect others in the research study or significantly impact the integrity of the research data. Such events would be considered a non-serious UP. For example, we will report occurrences of breaches of confidentiality, accidental destruction of study records, or unaccounted-for study drug.

Protocol Deviation: Any change, divergence, or departure from the IRB approved study procedures in a research protocol. Protocol deviations are designated as serious or non-serious and further characterized as:

- 1. Those that occur because a member of the research team deviates from the protocol.
- 2. Those that are identified before they occur, but cannot be prevented.
- 3. Those that are discovered after they occur

Non-compliance: The failure to comply with applicable IRB requirements, or regulatory requirements for the protection of human subjects. Non-compliance is further characterized as

- 1. Serious: Non-compliance that
 - a. Increases risks, or causes harm, to participants
 - b. Decreases potential benefits to participants
 - c. Compromises the integrity of the UMD IRB
 - d. Invalidates the study data
- 2. Continuing: Non-compliance that is recurring
- 3. Minor: Non-compliance that, is neither serious nor continuing.

8.2 INVESTIGATOR ASSESSMENT OF ADVERSE EVENTS

If a diagnosis is clinically evident, the diagnosis rather than the individual signs and symptoms or lab abnormalities will be recorded as the AE.

Laboratory abnormalities that are gradable per the toxicity table will be recorded as AEs or SAEs. All other laboratory abnormalities without clinical significance are not recorded as AEs or SAEs. Laboratory abnormalities that require medical or surgical intervention or lead to study drug interruption, modification or discontinuation must be recorded as an AE or SAE if applicable.

Laboratory assessments that are associated with signs and/or symptoms must be recorded as an AE or SAE if they meet the definition.

All AEs occurring from the time of ingesting one dose of the medications through the end of study will be documented, recorded, and reported. The Investigator will evaluate all AEs with respect to **Seriousness** (criteria listed above), **Severity** (intensity or grade), and **Causality** (relationship to study agent and relationship to research) according to the following guidelines.

8.2.1 Severity Grading

The investigator will grade the severity of each AE according to the "Division Of AIDS Table For Grading The Severity Of Adult And Pediatric Adverse Events" (Version 1.0, December, 2004; Clarification August 2009), which can be found at: http://rsc.techres.com/document/safetyandpharmacovigilance/table_for_grading_severity_of_adult_pediatric_a dverse_events.pdf

Please note that changes in hemoglobin will be graded only by the absolute value for this study and not by change from baseline.

Adverse Events not found in the Toxicity Table will be assessed for severity and classified into one of the categories below:

- **Grade 1 (Mild)**: Event requires minimal or no treatment and do not interfere with the participant's daily activities.
- **Grade 2 (Moderate)**: Event results in a low level of inconvenience or concern with the therapeutic measures. Moderate events may cause some interference with functioning.
- **Grade 3 (Severe)**: Event interrupts a subject's usual daily activity or functioning and may require systemic drug therapy or other treatment. Severe events are usually incapacitating.
- **Grade 4 (Potentially Life threatening)**: Events causing inability to perform basic selfcare functions OR Medical or operative intervention indicated to prevent permanent impairment, persistent disability, or death.

• Grade 5 (Death)

8.2.2 Causality

Causality (likelihood that the event is related to the study agent) will be assessed from the time study dosing begins until 30 days following the last dose considering the factors listed under the following categories:

Definitely Related

- reasonable temporal relationship
- follows a known response pattern
- clear evidence to suggest a causal relationship
- there is no alternative etiology

Probably Related

- reasonable temporal relationship
- follows a suspected response pattern (based on similar agents)
- no evidence of a more likely alternative etiology

Possibly Related

- reasonable temporal relationship
- little evidence for a more likely alternative etiology

Unlikely Related

• does not have a reasonable temporal relationship

OR

• good evidence for a more likely alternative etiology

Not Related

• does not have a temporal relationship

OR

• definitely due to an alternative etiology

Note: Other factors (e.g., dechallenge, rechallenge) should also be considered for each causality category when appropriate. Causality assessment is based on available information at the time of the assessment of the AE. The Investigator may revise the causality assessment as additional information becomes available.

8.3 SAFETY OVERSIGHT

Safety oversight will be conducted according to the Safety Monitoring Plan (see below) in a collaboration between the Principal Investigator (PI), lead Study Coordinator (SC) and the independent Medical Monitor.

8.3.1 Medical Monitor

An independent Medical Monitor (MM) has been appointed for oversight of safety in this clinical study. If at any point in the trial halting rules are met, the study team (PI and SC) will arrange a teleconference so that the event can be reviewed and the discussion documented. At the

end of each MM review meeting, the MM will be asked to provide a formal recommendation as to whether or not the protocol should be halted. A written summary of each MM review meeting will be provided to the MM and appropriate individuals. Participants on the MM teleconferences will include the MM, the PI and appropriate study team members.

8.4 SAFETY MONITORING PLAN

Ongoing Safety Monitoring by the Study Team: Cumulative safety data will be monitored by the study team (PI and SC). Upon recognition of any safety concerns, a teleconference may be held with the MM to discuss the concern. The PI will notify the MM and Gilead Clinical Safety Office (CSO) when enrollment begins and will provide verification of safety assessments to the MM and CSO. The ISM will review the viral kinetic, pharmacokinetic and resistance data to advise regarding continued study enrollment. The study team in collaboration with the study sponsor will then make a determination about whether the study enrollment needs to shut down.

Patient safety will be monitored by the PI and study team. Patient clinical data, safety data and virologic response will be monitored at weekly (or less frequently, as indicated by protocol activity) meetings by the study team and a summary report of these reviews will be retained as part of the study records. A complete evaluation of safety and efficacy data will be obtained when the first 20 patients complete 12 weeks of therapy. Thereafter, safety and data analysis will be performed every 12 weeks through completion of the study.

Additionally, the PI will be responsible for submitting the IRB Continuing Review package and will provide the necessary safety data for the FDA IND Annual Report.

8.5 SPECIFIC STUDY HALTING CRITERIA

8.5.1 Criteria to Pause Enrollment

- **Study will be paused** and the MM will be asked to review the data if 1: 3 participants experience virologic or therapeutic treatment failure while receiving treatment (see Dose Modification 3.4.1 and Treatment Failure Sections3.4.2)
- Dosing will be discontinued if 3 or more participants develop a similar related Grade 4 toxicity (excluding neutropenia, anemia, anorexia, weight loss and ALT and AST elevations). Further dosing will require review and approval after discussion with the MM. Grade 4 toxicities that result from patient non-compliance with medications for unrelated events will not be considered toward discontinuation.
- Enrollment will also be halted if the PI decides to stop or cancel the study or if the IRB or the FDA requests that the study be stopped.

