3.4.1 Dose Modification for SOF/VEL/VOX

Dose modifications will not be permitted. If a subject forgets to take the medication at the correct time, it may be taken later in the day; however, no more than a single dose should be taken on any calendar day. The subject should resume the standing dosing schedule on the next day. Any treatment interruption or discontinuation will be recorded including the reason for the interruption or discontinuation.

3.4.2 Treatment Failure / Drug Discontinuation

See also Criteria for premature withdrawal of subjects (2.20.2). Subjects will be considered treatment failures and will discontinue SOF/VEL/VOX FDC if they meet any of the following criteria while taking study drugs:

- HCV RNA greater than LLOQ after 2 prior consecutive HCV RNA values less than the LLOQ
- Greater than a 1 log₁₀ increase in HCV RNA from nadir
- Less than a 2 log₁₀ decline in HCV RNA after 4 weeks of treatment (unless >2 log drop would be below LLOQ)
- HCV RNA \geq LLOQ after 8 weeks of treatment

If any of these should occur in a patient who is currently on study drugs, the subject should return within one week for a confirmatory test. If the confirmatory test also meets the same criteria, the subject will be considered a treatment failure and should be discontinued from therapy. The anticipated clinical impact of discontinuation should be discussed in advance with the Medical Monitor (MM) if possible, particularly if discontinuation is thought to pose a risk to the overall clinical wellbeing of the subject. Those who are discontinued will continue to follow the general study schedule of assessments unless unwilling to do so, in which case they may be seen at least every 12 weeks for safety and research labs until the end of the study. Subjects will be followed closely for resolution of active laboratory abnormalities or adverse events which are considered related to the study agents prior to starting the revised schedule.

Subjects who meet any of the following laboratory criteria must stop all study medication(s):

- Elevation of ALT >5x OR AST >5x Day 0, confirmed by immediate repeat testing
- Abnormal elevation of ALT >3 x Day 0 *and* total bilirubin >2 x ULN, confirmed by immediate repeat testing
- Elevation of ALT >15 x ULN confirmed by immediate repeat testing
- Any Grade 3 or greater rash associated with constitutional symptoms
- Any Grade 4 event assessed as related to treatment with SOF/VEL/VOX FDC
- Pregnancy

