8.6 INVESTIGATOR REPORTING RESPONSIBILITIES

8.6.1 Adverse Events

Line listings, frequency tables, and other summary AE data will be submitted to the IND Sponsor when needed for periodic safety assessments, review of IND annual reports, review of IND safety reports, and preparation of final study reports.

8.6.2 Serious Adverse Events

Any SAE will be reported to the IRB per institutional guidelines. SAEs (regardless of relationship) must be reported to Gilead Drug Safety & Public Health (DSPH) Office within 15 calendar days of first becoming aware of the event. Reporting any unexpected fatal or life-threatening suspected adverse reactions to the Division of Antiviral Agents at the FDA no later than 7 calendar days after initial receipt of the information. Safety reporting to the FDA will be done within the reporting requirement under 21 CFR 312.32

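### The only count-based toxicity halting rule names Grade 4 alone, so a related death with no recorded Grade 4 phase does not count toward it

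*Combined protocol and SAP*

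**What the plan says.** Section 8.5.1 gives three criteria. The first pauses the study when three participants have virologic or therapeutic treatment failure on treatment; section 3.4.2 defines treatment failure by HCV RNA, so this is not a toxicity count. The second is the toxicity rule: "Dosing will be discontinued if 3 or more participants develop a similar related Grade 4 toxicity". It leaves out six named toxicities (neutropenia, anemia, anorexia, weight loss, ALT and AST elevations) and Grade 4 toxicities due to certain non-compliance. The third is a halt if the PI decides on one or the IRB or FDA asks for one.

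Meeting the second criterion has firm consequences. Dosing stops, and "Further dosing will require review and approval after discussion with the MM". Section 8.3.1 adds: "If at any point in the trial halting rules are met, the study team (PI and SC) will arrange a teleconference". The Medical Monitor (MM) is then asked for a formal recommendation on halting.

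Section 8.2.1 grades severity by an external table and adds: "Adverse Events not found in the Toxicity Table will be assessed for severity and classified into one of the categories below". The list that follows runs from Grade 1 to Grade 5. Grade 4 is potentially life-threatening and Grade 5 is death, as separate entries.

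**The concern.** A halting rule for severe related toxicity should count the worst outcome at least as readily as the one below it. Here the grade is given as 4, with nothing to say that higher grades are included, and the protocol's own list has a separate grade for death. No other text adds death to the count or sets a separate trigger for deaths.

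What is at stake is the automatic response: the stop in dosing, the approval needed to resume, and the mandatory MM review. A related death outside the count gets none of these from the rule itself. For a safety concern in general, section 8.4 says only: "Upon recognition of any safety concerns, a teleconference may be held with the MM to discuss the concern".

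**Working it through.** **Reading the text.** Take three participants with similar related fatal events that are not in the external table and not in an excluded category.

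| Recorded course | Counts under 8.5.1 as written? |
|---|---|
| Related Grade 4 toxicity, participant survives | Yes |
| Related Grade 4 toxicity, participant then dies | Yes, through the Grade 4 record |
| Related death, no Grade 4 phase recorded | No, read literally |

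If all three are of the last kind, the count is 0 and the rule is not met. For events that are in the external table, the grade of a fatal case cannot be determined here, because the documents do not reproduce the table.

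**What still operates for an uncounted death.**

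- Study-team review of safety data at weekly or less frequent meetings (8.4).
- Scheduled evaluation: "A complete evaluation of safety and efficacy data will be obtained when the first 20 patients complete 12 weeks of therapy", then every 12 weeks (8.4).
- SAE reporting to the IRB, and to the manufacturer within 15 days (8.6.2). Potential safety issues also go to the manufacturer within 15 days (8.6.3).
- Within 7 days: "Reporting any unexpected fatal or life-threatening suspected adverse reactions to the Division of Antiviral Agents at the FDA" (8.6.2).
- IRB reporting within 7 days for events, including deaths, that are unexpected, at least probably related and suggest greater risk than was known (8.9.1).
- The optional MM teleconference (8.4) and the discretionary PI, IRB or FDA halt (8.5.1).

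None of these is an automatic trigger. The duty in 8.8 to report related SAEs to the MM covers events after the follow-up period, so it is not a safeguard during treatment.

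**Illustrative size.** The plan states no operating characteristic for the rule, so there is no figure to reproduce for it. The nearest stated figures are the detection probabilities in section 4.1, and the same binomial model gives them: 1 − 0.95^120 = 0.998 (stated 99.8%) and 1 − 0.99^120 = 0.701 (stated 70%).

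Inputs: n = 120 (section 4.1) and threshold 3 (section 8.5.1). Two quantities are assumed because the documents give neither: q, the rate of one kind of similar related Grade 4 or 5 event, and h, the share of those that are deaths with no recorded Grade 4 phase. With X binomial:

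- Grade 4 or 5 counted: P(X ≥ 3; n = 120, p = q)
- Grade 4 only, as written: P(X ≥ 3; n = 120, p = q(1 − h))

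At q = 1%, counting both grades, P(0), P(1) and P(2) are 0.2994, 0.3629 and 0.2181, so P(X ≥ 3) = 1 − 0.8804 = 0.1196. As written with h = 50%, p = 0.5% and the three terms are 0.5480, 0.3304 and 0.0988, so P(X ≥ 3) = 1 − 0.9772 = 0.0228. The loss is 0.1196 − 0.0228, about 0.097.

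| q (assumed) | Grade 4 or 5 counted | As written, h = 5% | As written, h = 50% | Loss, percentage points |
|---|---|---|---|---|
| 0.5% | 2.3% | 2.0% | 0.4% | 0.3 to 1.9 |
| 1% | 12.0% | 10.7% | 2.3% | 1.3 to 9.7 |
| 2% | 43.1% | 39.9% | 12.0% | 3.2 to 31.2 |

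The rows with larger q should be read with caution. Sections 1.8 and 6.1.3 report no clinical safety issue in over 2600 subjects. Even a related-death rate of 0.25% would imply 0.0025 × 2600 = 6.5 deaths there, and the chance of seeing none would be 0.9975^2600, about 0.15%.

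**The case against.** The strongest reply is that a sensible investigator would treat a related death as at least Grade 4, that most fatal toxicities pass through a recorded Grade 4 phase, and that the reporting routes would bring any related death to people who can halt the trial. Most of this stands and is why the point is minor. It does not remove the gap, because a rule that already fixes the number, similarity, relatedness and exclusions should not depend on inference for its gravest case.

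It is also fair to say that the change does little for a first or second related death, since the count stays at three. That is correct. The change only brings the stated rule into line with its evident subject.

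A reader might infer that the drafters left deaths out on purpose, because section 3.4.2 uses wider wording for another event: "Any Grade 3 or greater rash associated with constitutional symptoms". The documents do not support that. The next item in the same list refers to related events of Grade 4 with no wider wording. The Study Summary's primary safety endpoint likewise speaks of grades 3 and 4, so Grade 4 often serves as the top working grade. The reference to fatal reactions in 8.6.2 concerns FDA reporting and says nothing about the halting rule.

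A reader might also infer that related deaths go unreviewed, or that no fatal case can count. Neither follows, given the routes listed above and the fact that a recorded Grade 4 phase counts.

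**Conclusion.** The point holds on the wording. The only count-based toxicity rule names Grade 4 alone, and read literally it leaves out related deaths with no recorded Grade 4 phase. This is firm for events graded by the protocol's own list; for events in the external table it is undetermined. No claim is made about why the wording is as it is.

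The size is small. At an assumed event rate of 1%, with 5% to 50% of events being uncounted deaths, the rule fires 1.3 to 9.7 percentage points less often. These figures rest on assumed rates, on independent participants, and on all events being similar enough to count together. They show how the wording behaves and do not predict deaths in this trial. The efficacy analysis is unaffected. Severity: minor.

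**What to change.** In section 8.5.1, second criterion, change the trigger to *similar related Grade 4 or Grade 5 toxicity*. State that the six listed exclusions apply to Grade 4 only; otherwise a fatal event in an excluded category, such as a fatal neutropenia, would still be left out. Keep the count of three and the rest of the criterion.

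The cost is a wording change in the protocol, with no added visits, tests or participants. The downside is a slightly more sensitive trigger: under the assumptions above, it fires more often by the same amounts as the losses in the table.
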